5.3. Withdrawal/Stopping Criteria

The primary reason for the subject discontinuing from the study will be recorded in the Case Record Form. The investigator must determine the primary reason for discontinuation. The end of study/early discontinuation procedures must be performed at the time of discontinuation from the clinical study.

The subject **must** be discontinued from the study for any of the following reasons:

1. A subject is significantly non-compliant with treatment or the requirements of the protocol;
2. Lost to follow up;
3. Subject's decision not to participate any further (withdrawal of consent);
4. In the investigator's opinion, it is in the subject's best interest;
5. Subjects experience a protocol-defined asthma exacerbation;
6. The study is terminated by the Sponsor or designee;
7. Pregnancy (Subject should notify investigator immediately on becoming pregnant).

A subject may withdraw from study treatment at any time at his/her own request, or may be withdrawn at any time at the discretion of the investigator for safety, behavioural or administrative reasons.

The reason(s) for subjects not completing the study will be recorded in the Case Report Form (CRF), and that the investigator must document, if applicable, the reason (if specified by the subject) for withdrawal of consent. The end of study/early discontinuation procedures must be performed at the time of discontinuation from the clinical study.

The following actions must be taken in relation to a subject who fails to attend the clinic for a required study visit:

- The site must attempt to contact the subject and re-schedule the missed visit as soon as possible.
- The site must counsel the subject on the importance of maintaining the assigned visit schedule and ascertain whether or not the subject wishes to and/or should continue in the study based on previous non-compliance.
- In cases where the subject is deemed 'lost to follow up', the investigator or designee must make every effort to regain contact with the subject (where possible, 3 telephone calls and if necessary a certified letter to the subject's last

known mailing address or local equivalent methods). These contact attempts should be documented in the subject's medical record.

- Should the subject continue to be unreachable, only then will he/she be considered to have withdrawn from the study with a primary reason of "Lost to Follow-up".

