5.4. Subject and Study Completion

A completed subject is one who has completed all visits of the study.

The end of the study is defined as the last subject's last visit.

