7.1. Time and Events Table

ACTIVITY	Visit 0	Visit 1	Visit 2	Visit 3	Visit 4	Visit 5	Visit 6 (or Early Withdrawal)
Study Week (Visit Window)	0	4w±1	8w±1	12w±1	16w±1	20w±1	24w±1
Informed consent	x						
Randomization/Allocation of clusters	x						
Subject Demography	x						
Medical history	x						
Verification of inclusion/exclusion criteria	x						
Efficacy Evaluation							
Verification of withdrawal criteria		x	x	x	x	x	x
Issue diary record cards	x	x	x	x	x	x	
Collect/Review diary record cards		x	x	x	x	x	x
Compliance assessment		x	x	x	x	x	x
Asthma control Test (ACT) score	x	x	x	x	x	x	x
AQLQ(S)	x						x
Lung function Test	x						x
Safety Evaluation							
Adverse event assessment ¹	x	x	x	x	x	x	x

1. Serious AEs will be recorded from the time the consent form is signed until the follow-up visit. All AEs will be recorded from the start of study treatment until the follow-up visit.

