4. ANALYSIS POPULATIONS

Population	Definition / Criteria	Analyses Evaluated
Intent-To-Treat (ITT)	
 All subjects who signed informed consent form, were randomised and who had at least one post-baseline assessment on primary endpoints, second endpoints, and/or exploratory endpoints. The ITT population will be the primary population of interest. 	Study Population Efficacy
Per-Protocol (PP)	
 All subjects in the ITT population with no major protocol deviations and with $\geq 80\%$ treatment compliance and diary compliance. The PP population will not be analyzed if this population comprises more than 95% or less than 50% of the ITT population. Only the primary efficacy variables will be analyzed using the PP population. 	Efficacy
Safety	
 All subjects who are enrolled into the study and who have at least one DRC assessment. 	Safety

Refer to [Appendix 8](#): List of Data Displays which details the population used for each display.

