7.2.2. Analysis Methods

All secondary endpoints will be confined to the ITT population. The continuous efficacy endpoints will be summarized by mean, standard deviation (SD), median, minimum and maximum according to scheduled visits. Time to event endpoint will be summarized by median time, 95% confidence interval of median time, lower and upper quantiles and range.

Continuous efficacy endpoints will be analysed using analysis of covariance (ANCOVA) and adjusted for centre as a random effect.

For mean daytime and night-time symptom score and mean morning and evening PEF, the mean values will be based on the available data on the diary card over each visit assessment period. No imputations will be performed on missing data. The mean values will be considered missing if less than 14 days are recorded in each visit assessment period. A Mixed Model Repeated Measures (MMRM) will be used with covariates of treatment, centre, type of baseline controller (ICS vs. ICS/LABA), gender and age, with the centre as a random factor. The results will be presented as LS mean (SE), 95% confidence interval for LS mean, treatment difference, 95% confidence interval for treatment difference and P-value by visit.

The example SAS codes are as below:

```
proc mixed data=input_data;
class invsite rndgrp visit subjid blcontrol gender;
model endpoint=rndgrp actbl blcontrol gender age/ ddfm =kr;
random intercept/subject= invsite;
repeated visit / subject=subjid type=un;
lsmeans rndgrp*visit / cl diff e;
ods output lsmeans=lsmeans;
ods output diffs=diffs;
run;
quit;
```

where `input_data` is the name of the input dataset and `endpoint` is the endpoint variable. In terms of the covariates `rndgrp`, `actbl`, `blcontrol`, `gender` and `age` are variables for randomised treatment code, baseline ACT total score, type of baseline controller, gender and age respectively. For random effect, `invsite` is variable for centre. For repeated measures, `visit` is variable for visit number and `subjid` is variable for subject's ID.

The AQLQ(S) contains 32 items in four domains: activity limitation (11 items), symptoms (12 items), emotional function (5 items) and environmental stimuli (4 items). The following items are included in each of the 4 domains:

- Symptoms: 6, 8, 10, 12, 14, 16, 18, 20, 22, 24, 29, 30
- Activity Limitation: 1, 2, 3, 4, 5, 11, 19, 25, 28, 31, 32
- Emotional Function: 7, 13, 15, 21, 27
- Environmental Stimuli: 9, 17, 23, 26

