The response format consists of a seven-point scale where a value of 1 indicates “total impairment” and a value of 7 indicates “no impairment”. The total AQLQ(S) score is the mean of all 32 items in the questionnaire and each individual domain score is calculated as the mean of the items within that domain. Hence, the total and domain scores are also each defined on a range from 1 to 7 with higher scores indicating a higher quality of life.

For the total AQLQ(S) score, the score for a subject at any time point will only be calculated if at least 90% of the questions were answered (calculated as the mean of those non-missing questions). If fewer than 90% of the questions were answered then the mean score for that subject at that time point will be considered missing.

For each individual domain of the AQLQ(S) score, the score for a subject at any time point will only be calculated if at least 90% of the questions for that domain were answered (calculated as the mean of those non-missing questions). If fewer than 90% of the questions were answered for that domain then the mean score for that subject and domain at that time point will be considered missing.

The analysis of changing from baseline to the end of study in FEV1 and AQLQ(S) score will only include those who complete the study and change from baseline will be calculated as the difference between baseline visit and Visit 6.

For FEV1 and AQLQ(S) changing from baseline, a mixed model will be used with covariates of treatment, centre, type of baseline controller (ICS vs. ICS/LABA), gender and age, with the centre as a random factor. The results will be presented as LS mean (SE), 95% confidence interval for LS mean, treatment difference, 95% confidence interval for treatment difference

The example SAS codes are as below:

```
proc mixed data=input_data;
class invsite rndgrp blcontrol gender;
```

```

model epchbl=rndgrp actbl blcontrol gender age/ ddfm =kr;
random intercept/subject= invsite;
lsmeans rndgrp/ cl diff e;
ods output lsmeans=lsmeans;
ods output diffs=diffs;
run;
quit;

```

where `input_data` is the name of the input dataset and `epchbl` is the endpoint variable changing from baseline. In terms of the covariates `rndgrp`, `actbl`, `blcontrol`, `gender` and `age` are variables for randomised treatment code, baseline ACT total score, type of baseline controller, gender and age respectively. For random effect, `invsite` is variable for centre.

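### The FEV1 and AQLQ(S) change analyses are limited to subjects who completed every visit, which as written drops valid Visit 6 values and leaves early-withdrawal values unused

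*SAP*

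**What the plan says.** SAP 7.2.2 opens with "All secondary endpoints will be confined to the ITT population", and Protocol 9.4.2 says the same. SAP section 4 does not make completion a condition of ITT membership: it takes in consented, randomised subjects "who had at least one post-baseline assessment on primary endpoints, second endpoints, and/or exploratory endpoints".

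Later in SAP 7.2.2 a narrower rule appears: "The analysis of changing from baseline to the end of study in FEV1 and AQLQ(S) score will only include those who complete the study". The same sentence takes the change from Visit 0 to Visit 6 and does not mention a withdrawal value. Protocol 9.4.2 contains no such restriction. The SAP gives no reason for it and plans no sensitivity analysis for these two endpoints. SAP 2.1 reports no departure from the protocol's analysis beyond extra sensitivity and supportive work on the primary endpoint.

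On who counts as a completer, Protocol 5.4 says "A completed subject is one who has completed all visits of the study", and SAP 10.5.1 repeats this definition.

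On what is measured at exit, Protocol 7.1 and SAP 10.2.1 mark AQLQ(S) and the lung function test at Visit 0 and in a final column shared by Visit 6 and early withdrawal. Protocol 5.3 adds: "The end of study/early discontinuation procedures must be performed at the time of discontinuation from the clinical study". The same section lists, among the reasons for mandatory discontinuation, "Subjects experience a protocol-defined asthma exacerbation".

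**The concern.** Two groups with usable data fall outside the analysis. The first attended Visit 6 but missed an interim visit. Their change from baseline can be calculated in full, and nothing in a Visit 0 to Visit 6 difference depends on the visits between. The second left early but had FEV1 and AQLQ(S) measured on exit, as the protocol requires.

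The second exclusion may also be related to prognosis, because exacerbation is a listed reason for leaving. If exits differ between ACT-guided and usual-care centres, or if leavers in one arm are worse off than leavers in the other, the comparison among completers no longer reflects the arms as randomised. Two secondary endpoints are at stake; the primary analysis is not affected.

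**Working it through.** **The plan's own figure.** The documents size the trial only for the primary endpoint (Protocol 9.2.1): 29% against 44%, ICC 0.01, 35 evaluable subjects per centre, 6 centres per arm, 80% power, two-sided 0.05.

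- Design effect: 1 + (35 − 1) × 0.01 = 1.34.
- Unclustered size per arm, unpooled variance: (1.960 + 0.842)² × (0.29 × 0.71 + 0.44 × 0.56) / 0.15² = 157.8.
- Clustered total: 2 × 157.8 × 1.34 = 422.9, or 6.04 centres per arm, against 420 and 6 stated.
- Dropout: 35 / 0.8 = 43.75, rounded up to 44 per centre; 44 × 12 = 528.

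The stated figures reproduce. There is no corresponding calculation for FEV1 or AQLQ(S).

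**Subjects excluded at the planned dropout.** 528 × 0.20 = 105.6, or 528 − 420 = 108 with the plan's rounding. So 106 to 108 subjects, about 20%, would leave before Visit 6. The documents do not say how many of them would attend a withdrawal assessment. Subjects excluded for a missed interim visit come on top; the documents give no rate for that.

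**Shift in the treatment difference.** Let d be the share of an arm that leaves and D the amount by which leavers' change is worse than completers' change. The arm mean over all subjects is the completers' mean minus d × D. Completers therefore overstate each arm by d × D, and the difference (ACT minus usual care) shifts by

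D × (d_ACT − d_UC).

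Assumptions, not in the documents: D and the split of exits. D = 0.5 is taken from the AQLQ change that Protocol 7.3.2 treats as clinically important; the range shown is 0.25 to 1.0.

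| Exits, ACT / usual care | D = 0.25 | D = 0.5 | D = 1.0 |
|---|---|---|---|
| 20% / 20% | 0 | 0 | 0 |
| 15% / 25% | −0.025 | −0.05 | −0.10 |
| 10% / 30% | −0.05 | −0.10 | −0.20 |

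Reversing the split reverses the sign. If usual care loses more subjects, a benefit of ACT guidance is understated; if the ACT arm loses more, it is overstated. Equal exit rates protect the comparison only if D is also equal: at 20% in both arms with deficits of 0.25 and 0.75, the shift is 0.20 × 0.50 = 0.10 in size.

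For FEV1 the same formula applies, but the documents give no SD or target difference against which to judge a result.

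**The case against.** **ITT.** A reader might infer that the SAP contradicts itself on the analysis population. It does not, strictly. Confining an analysis to ITT sets an outer limit, and completers are a subset. SAP 10.5.1 includes withdrawn subjects' available data except where another rule applies, and the completer sentence can be read as that exception. What stands is a restriction that the protocol lacks, added without explanation or record.

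**Selection on poor outcome.** A reader might also infer that the excluded subjects are, by design, those who did badly. The documents do not settle this. Protocol 5.3 lists exacerbation as a reason for mandatory discontinuation. Protocol 7.3.3, however, describes treating an exacerbation during the treatment period, counts separate steroid courses as separate events and collects details at the next visit. SAP 7.3 models a count of exacerbations per subject. These sections handle exacerbations as if subjects continue, and they must be reconciled with 5.3. Other reasons for exit, such as pregnancy or termination by the sponsor, have no evident link to prognosis.

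**Loss from missed visits.** One could multiply the 422 expected finishers by (1 − q)⁵ for five interim visits: q of 2%, 5% or 10% leaves 382, 327 or 249. The arithmetic is right, but no document supports any q or independence between visits, and Protocol 5.3 asks sites to reschedule missed visits. The SAP may also have meant only that a Visit 6 value must exist. These figures do not show an expected loss.

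**Using withdrawal values.** Placing them in the main analysis would turn a Week 24 change into a mixture of last values taken at different times, some perhaps during an acute episode. A supportive completer analysis would not cure that. In addition, Protocol 7.3.2 names only Visits 0 and 6 for these measures, so collection at exit rests on the schedule and on 5.3. This objection stands, and it is why withdrawal values belong in a sensitivity analysis.

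**Conclusion.** The point holds as a wording fault with an easy remedy. As written, the rule discards valid Visit 6 values for a reason unrelated to the endpoint, leaves required exit measurements unused, and narrows the protocol's analysis without saying so.

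The planned exclusion is about 20% of enrolled subjects, if the 20% dropout assumption holds and dropouts have no Visit 6 value. The bias is conditional. On the AQLQ scale it is zero when exit rates and leavers' deficits match across arms, and 0.05 to 0.10 in size for the 15%/25% and 10%/30% splits at a deficit of 0.5. That is one tenth to one fifth of the 0.5-point threshold. The documents cannot show in advance whether exits will differ. For FEV1 the importance of a shift cannot be judged from the documents.

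**What to change.** In SAP 7.2.2, replace the completer sentence with:

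> All ITT subjects with a baseline and a Visit 6 value are included, whether or not interim visits were missed.

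Because Visit 6 and early withdrawal share a schedule column, and SAP 10.5.1 leaves open how withdrawal visits are slotted, state that Visit 6 here means the Week 24 visit.

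Add a sensitivity analysis that also includes early-withdrawal values for subjects who left before Visit 6. Report it as a last-available-value analysis and not as a Week 24 change. Record both changes in SAP 2.1. Separately, the passages on exacerbation in Protocol 5.3, Protocol 7.3.3 and SAP 7.3 must be reconciled.

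The cost is SAP wording and a little more analysis; no new data or subjects are needed. Some limits remain. The main analysis still omits subjects without a Visit 6 value. Withdrawal values are measured before Week 24 and may reflect an acute episode, and subjects lost to follow-up may have none.

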9.4.2. Secondary Analyses

All secondary endpoints will be confined to the ITT population.

Continuous efficacy endpoints will be analyzed using analysis of covariance (ANCOVA) and adjusted for centre as a random effect. For daytime and night-time symptom score, the same method (ANCOVA adjusted by centre) will be used if the parametric model assumptions hold. The assumptions of normality and homogeneity of variance will be assessed by inspection of normal probability plots and residual plots. If these assumptions are not met, alternative methods (e.g., nonparametric methods) may be performed in order to assess the robustness of the conclusions from the primary analysis.

For time to event endpoint, stratified log-rank test and Cox regression analysis will be performed with centre, type of baseline controller (ICS alone vs. ICS/LABA), gender and age as the stratification factors. Kaplan-Meier methodology will be used to estimate median time for each treatment arm. Kaplan-Meier curves will be constructed to provide a visual description of the difference between the two treatment arms.

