5.2. Baseline Definitions

For primary endpoint, baseline will be the measurements taken at visit 0. For secondary endpoints, baselines of FEV1 and AQLQ(S) will be the measurements taken at visit 0; for symptom score and PEF, baselines are unavailable since the data will be collected daily using diary cards from the first day of asthma treatment and baseline assessments before treatment will not be conducted.

Unless otherwise stated, if baseline data is missing, no derivation will be performed and baseline will be set to missing.

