where input_data is the name of the input dataset and response is the response variable. In terms of the covariates rndgrp, actbl, actblsq, blcontrol, gender, age and visit are variables for randomised treatment code, baseline ACT total score, baseline ACT total score squared, type of baseline controller, gender, age and visit number, respectively. For repeated measures, visit is variable for visit number and subjid is variable for subject's ID.

This analysis will be performed for the ITT and PP populations.

- Percentage of subjects who have an ACT total score ≥ 20 and an improvement of more than 3 points in ACT total score.

The following endpoints will be analysed as sensitivity analyses.

- ✓ Percentage of subjects who have an ACT total score ≥ 20 and an improvement of more than 3 points in ACT total score at Week 12. Subjects with missing data at Week 12 will be set as non-responders.
- ✓ Percentage of subjects who have an ACT total score ≥ 20 and an improvement of more than 3 points in ACT total score at Week 24. Subjects with missing data at Week 24 will be set as non-responders.
- ✓ Percentage of subjects who have an ACT total score ≥ 20 and an improvement of more than 3 points in ACT total score at Weeks 16 and 20 and 24. Subjects with missing data at Weeks 16, 20 or 24 will be set as non-responders.

These endpoints will be analysed using the same model as defined for primary endpoint (GLMM). A supportive analysis will be conducted to analysis the percentage of subjects who have an ACT total score ≥ 20 and an improvement of more than 3 points in ACT total score, using the same GEEs method as mentioned above. All non-missing data from visits with scheduled ACT assessments (Weeks 4, 8, 12, 16, 20 and 24) will be used.

These analyses will be performed for the ITT and PP populations.

- Change from baseline in ACT total score in post-baseline visits.

A Mixed Model Repeated Measures (MMRM) will be used with covariates of treatment, baseline ACT total score, centre, type of baseline controller (ICS alone vs. ICS/LABA), gender, age, visit, treatment-by-visit interaction and treatment-by-baseline ACT total score, with centre as a random effect. The least squares (LS) mean and LS mean change from baseline for each treatment and the estimated LS mean change from baseline treatment difference will be presented at each visit together with the 95% confidence interval for the mean difference and P-value.

The example SAS codes are as below:

```

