proc mixed data=input_data;
class invsite rndgrp visit subjid blcontrol gender;
model actchbl=rndgrp actbl blcontrol gender age visit rndgrp*visit
rndgrp*actbl/ ddfm =kr;
random intercept/subject= invsite;
repeated visit / subject=subjid type=un;
lsmeans rndgrp*visit / cl diff e;
ods output lsmeans=lsmeans;
ods output diffs=diffs;
run;
quit;
```

where input_data is the name of the input dataset and actchbl is change from baseline in ACT score. In terms of the covariates rndgrp, actbl, blcontrol, gender, age and visit are variables for randomised treatment code, baseline ACT total score, type of baseline controller, gender, age and visit number, respectively. For random effect, invsite is variable for centre. For repeated measures, visit is variable for visit number and subjid is variable for subject's ID.

This analysis will be performed for the ITT and PP populations.

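### The FEV1 and AQLQ(S) change models omit the outcome's own Visit 0 value, and SAP 7.2.2 text and code disagree on baseline ACT

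*SAP*

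**What the plan says.** **FEV1 and AQLQ(S), text (SAP 7.2.2).** The outcome is the change between Visit 0 and Visit 6 in subjects who complete the study: "a mixed model will be used with covariates of treatment, centre, type of baseline controller (ICS vs. ICS/LABA), gender and age", with centre random. No baseline score of any kind is listed.

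**FEV1 and AQLQ(S), code (SAP 7.2.2).** "model epchbl=rndgrp actbl blcontrol gender age/ ddfm =kr". The SAP defines actbl as baseline ACT, so the code has one baseline score, and it is not the outcome's own.

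**Availability.** SAP 5.2: "baselines of FEV1 and AQLQ(S) will be the measurements taken at visit 0". The schedule of activities has both tests at Visit 0.

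**The SAP's other change endpoint (SAP 7.1.3).** For change in ACT: "A Mixed Model Repeated Measures (MMRM) will be used with covariates of treatment, baseline ACT total score, centre". The code agrees: "model actchbl=rndgrp actbl blcontrol gender age visit rndgrp*visit". That model adjusts for its own baseline.

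**Diary endpoints (SAP 7.2.2).** The code is "model endpoint=rndgrp actbl blcontrol gender age/ ddfm =kr", while the text lists treatment, centre, controller type, gender and age without baseline ACT. SAP 5.2 states that symptom scores and PEF have no baseline.

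**General label.** Protocol 9.4.2: "Continuous efficacy endpoints will be analyzed using analysis of covariance (ANCOVA) and adjusted for centre as a random effect". SAP 7.2.2 repeats it. Neither names a baseline covariate. The default adjustment set in Protocol 9.4 is centre, controller type, gender and age.

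**The concern.** A change score fixes the slope on the outcome's baseline at 1. If the true slope is below 1, the residual variance is larger than it need be. In addition, a fraction (1 - slope) of any chance baseline difference between the arms stays in the treatment estimate with opposite sign. With 12 randomised centres such differences are plausible. Baseline ACT removes only the part that ACT predicts.

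The text/code mismatch is a separate, smaller matter. Someone following the text and someone following the code would fit different models for six secondary endpoints: FEV1, AQLQ(S), two symptom scores and two PEF measures. The missing own baseline concerns FEV1 and AQLQ(S) only, because the diary endpoints have none.

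**Working it through.** **Plan's own figure.** The plan states no SD, correlation or power for FEV1 or AQLQ(S), so there is nothing to reproduce for these endpoints. Protocol 9.2.1 supplies the layout: 35/(1 - 0.20) = 43.75, rounded up to 44 per centre. That is 12 x 44 = 528 enrolled and 12 x 35 = 420 evaluable, or 210 per arm. I use 12 centres of 35 as the completer set.

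**Assumed inputs (none in the documents).** Visit 0 SD = 1; Week 24 SD = k; baseline-Week 24 correlation r; correlation a between ACT and the outcome's own baseline. ACT is independent of the Week 24 value given own baseline. The same correlations hold within and between centres, so the SE scales with the square root of the residual variance.

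**Formulas.** The slope of Week 24 on baseline is rk.
- Own baseline in the model: k²(1 - r²).
- Change score with baseline ACT only, as coded: k²(1 - r²) + (1 - a²)(1 - rk)².

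| k | r | a | as coded | own baseline added | ratio | SE |
|---|---|---|---|---|---|---|
| 1 | 0.5 | 0.5 | 0.9375 | 0.75 | 0.800 | -10.6% |
| 1 | 0.5 | 0.7 | 0.8775 | 0.75 | 0.855 | -7.6% |
| 1 | 0.8 | 0.5 | 0.3900 | 0.36 | 0.923 | -3.9% |
| 1 | 0.8 | 0.7 | 0.3804 | 0.36 | 0.946 | -2.7% |
| 1 | 0.9 | 0.5 | 0.1975 | 0.19 | 0.962 | -1.9% |
| 1 | 0.9 | 0.7 | 0.1951 | 0.19 | 0.974 | -1.3% |
| 0.8 | 0.5 | 0.5 | 0.7500 | 0.48 | 0.640 | -20.0% |
| 0.8 | 0.8 | 0.7 | 0.2965 | 0.2304 | 0.777 | -11.8% |
| 1.25 | 0.5 | 0.5 | 1.2773 | 1.1719 | 0.917 | -4.2% |
| 1.25 | 0.8 | any | 0.5625 | 0.5625 | 1.000 | 0 |

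The last row is zero because rk = 1: the change score then already uses the right slope.

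**If the text is followed instead (no baseline ACT).** Set a = 0 and k = 1. The ratio is (1 + r)/2, which is 0.75 at r = 0.5 (SE -13.4%) and 0.90 at r = 0.8 (SE -5.1%).

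**Simulation check.** 12 centres of 35, REML random centre intercept, k = 1, ICC 0.01, baseline ACT in both models. For (r, a) = (0.5, 0.5), (0.5, 0.7), (0.8, 0.5) and (0.8, 0.7), adding own baseline multiplied the mean reported SE by 0.902, 0.934, 0.960 and 0.978. It multiplied the actual SD of the estimate by 0.894, 0.936, 0.965 and 0.985, so the gain is not confined to the reported SE. In a separate simulation on centre-level adjusted means (r = 0.6), type I error was about 5% with and without the term.

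**Chance imbalance.** The SD of the between-arm difference in own baseline not explained by ACT is sqrt(2(1 + 34 x ICC)/210) x sqrt(1 - a²).
- ICC 0.01: 0.113 x 0.866 = 0.098 (a = 0.5); 0.113 x 0.714 = 0.081 (a = 0.7).
- ICC 0.05: 0.139 and 0.115.

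Multiplying by (1 - rk) gives the typical amount left in the estimate. With k = 1 and r = 0.5-0.8 this is 0.049 down to 0.016 Visit 0 SD at ICC 0.01, and 0.069 down to 0.023 at ICC 0.05. The protocol's ICC of 0.01 was set for the well-control rate, so both values are assumptions for these outcomes.

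**The case against.** **The gain may be close to nothing.** This stands as a limit on the size. Equal variances are not a neutral default. Entry requires ACT below 20 (Protocol 5.1), and the exclusion for severe, unstable asthma cites ACT below 12 (Protocol 5.2). That could narrow the Visit 0 spread of a related outcome such as AQLQ(S), which means k above 1 and a smaller gain. Relaxing the conditional independence of ACT also matters: at k = 1, r = 0.8, a = 0.7 and an ACT-Week 24 correlation of 0.4, the variance ratio is 0.999. A reader might take 3-11% as a general bound; it holds only under the equal-variance and independence assumptions.

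**The method label is not contradicted.** A reader might infer that the SAP breaks a promise of ANCOVA. The documents do not support that. "Continuous efficacy endpoints will be analysed using analysis of covariance (ANCOVA) and adjusted for centre as a random effect" names no own-baseline covariate, nor does Protocol 9.4, and the coded model does contain continuous covariates (age and baseline ACT). The label alone does not require the outcome's own baseline.

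**Nothing is invalid.** A reader might also infer a biased treatment effect. Over randomisations the change-score estimate is unbiased. The imbalance argument concerns the single realised allocation.

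What survives is that the term is free of data cost, the SAP already uses own-baseline adjustment for its ACT-change endpoint, and text and code disagree on baseline ACT.

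**Conclusion.** The omission and the text/code mismatch are certain from the documents. The consequence is modest: lost precision and weaker protection against chance baseline imbalance on two secondary endpoints, with no effect on the primary result or the sample size.

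The size depends on quantities the documents do not give. With baseline ACT in the model and ACT independent of Week 24 given own baseline, the SE reduction is about 3-11% for equal variances (r = 0.8-0.5, a = 0.7-0.5) and about 1-2% at r = 0.9. It is about 0-20% at r = 0.8-0.5 if the SD ratio is anywhere from 1.25 to 0.8. The share of a chance baseline difference left in the estimate is (1 - slope); this equals (1 - r) only when the two variances are equal.

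This is a worthwhile low-cost improvement plus a wording correction, not an error that threatens the trial's conclusions.

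**What to change.** Before database lock:

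1. In SAP 7.2.2, add Visit 0 FEV1 as a continuous covariate to the FEV1 model and Visit 0 AQLQ(S) to the AQLQ(S) model, in both text and code. If domain scores are analysed, use the same domain's Visit 0 score.
2. Make text and code agree on baseline ACT in the FEV1/AQLQ(S) model and in the diary-endpoint model.
3. Declare the added terms in SAP 2.1, including baseline ACT if it is kept. They go beyond the covariates in Protocol 9.4, and SAP 2.1 currently reports no change beyond added analyses of the primary endpoint.

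Cost: one already collected covariate per model and some SAP wording. No subject drops out, because the change score already needs the Visit 0 value.
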